#### **ARM B (7+3) + Midostaurin**

- **Cytarabine** 100 mg/m^2/day will be administered by continuous IV infusion for a total of 7 days beginning Day 1
- **Daunorubicin** 90 mg/m^2/day will be administered IV per package insert or per institutional guidelines or over 30-60 minutes Days 1,2,3.
- **Midostaurin** 50 mg orally BID x 14 days beginning on day 8

If there is a delay in starting FLT3 inhibitors in Arm A or Arm B (due to obtaining drug, i.e. insurance, formulary, etc.), the FLT3 inhibitor will need to stop after Day 21 dose (i.e., Day 21 or Day 22 [if FLT3 inhibitor started on Day 9]). No missed doses will be made up.

**NOTE:** If second cycle of induction is needed, daunorubicin dose will be decreased to 45 mg/m^2/day IV Days 1,2,3.

---

A bone marrow aspirate/biopsy will be performed on all patients on Day 21 (+/-1 day window; delays due to holidays, weekends, or other unforeseen circumstances will be permitted) to determine the need for a second induction cycle. If the marrow aspirate/biopsy is inadequate to make a determination, consider repeating the bone marrow assessment in 5-7 days.

**Arm A + Gilteritinib:** If second cycle of induction is planned, treatment will begin after Day 28 (i.e.,  $\geq 7$  days after completing gilteritinib) but no later than Day 45.

**Arm B + Midostaurin:** If second cycle of induction is planned, treatment will begin after Day 24 (i.e.,  $\geq 3$  days after completing midostaurin) but no later than Day 45.

A repeat bone marrow aspirate/biopsy should be done to assess for response and MRD status upon peripheral blood count recovery (Absolute Neutrophil Count (ANC)  $\geq 1000/\text{mm}^3$ , platelets  $\geq 100,000/\text{mm}^3$ ) but no later than Day 60 after initiation of the first cycle of induction therapy for patients who receive 1 cycle of induction or no later than Day 60 after initiation of the second cycle of induction therapy (i.e., Day 84-105) for patients who receive 2 cycles of induction (MRD sample will be obtained by Day 60 on all patients even if counts have not recovered. The only exception is a patient who has been declared a relapse based on blood counts).

Patients who do not achieve a CR or CR with incomplete hematologic recovery (CRi) by Day 60 if one cycle and Day 84-105 if 2 cycles of induction therapy will be removed from study.

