Patients who achieve CR or CRi can proceed to post remission consolidation therapy on study (if otherwise eligible) or may proceed to allogeneic transplant if desired. Patients who do not achieve CR/CRi are removed from study.

Patients who go to transplant or any other non-protocol leukemia directed therapy will complete an end of treatment visit, and will be followed for relapse and survival only.

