### 7.2 Duration of Follow-Up

Patients will be followed for adverse events for 30 days after their last dose of study medication. However, if a patient experiences an adverse event >30 days after their last dose of study medication that is felt to be, in the opinion of the investigator, possibly, probably or definitely related to study therapy, the adverse event should be reported.

**NOTE:** Pregnancy within 180 days for WOCBP and for 120 days for a female partner of child-bearing potential after the final study drug administration will be reported and followed per Section 8.6.

Patients should be followed every 3 months from end of treatment for 2 years, then every 4 months for 1 year, then every 6 months for 1 year, then annually for progression and survival until death or study closure (+/- 1 month) whichever comes first. Patients should be seen up to the 2 year point at the treating institution. If the patient is unable to be seen at the treating institution, copies of office visit notes including labs with local oncologist should be obtained until year 5 per schedule above. Initiation of all anticancer therapy for current remission and first anticancer therapy for relapse will be documented.

If a patient is removed from treatment for reason(s) other than progression or full consent withdrawal, follow for survival/relapse until death or study closure.

For patients who are registered with tissue submitted for the study and are FLT3 negative or other condition, no further information will be collected after baseline demographics, sample submission, sample results and final diagnosis. For eligible patients randomized to the trial, but do not receive any protocol therapy, baseline, safety [as applicable] and end of treatment follow-up information per Section 10 will also be collected.

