### 7.3 Criteria for Removal from Study Treatment

A genuine effort will be made to determine the reason(s) why a patient fails to return for the necessary visits or is discontinued from the trial, should this occur. It will be documented whether or not each patient completed the clinical study. If for any patient study treatment or observations were discontinued, the reason will be recorded on the appropriate electronic case report form. Reasons that a patient may discontinue treatment in a clinical study are considered to constitute one of the following:

1. If the patient has already initiated midostaurin or gilteritinib therapy and CNS involvement is detected, the patient may either come off protocol therapy immediately or complete therapy through Day 21 then will be removed from protocol treatment.
2. Failure to achieve CR or CRi after 2 cycles of induction.

3. Patient requires treatment with therapy not allowed per protocol, or patient goes on to receive HSCT.
4. Recurrence of disease or documented progression of disease.
5. Intercurrent illness that prevents further administration of treatment per investigator discretion.
6. Unacceptable adverse events.
7. Investigator and/or patient discontinue chemotherapy.
8. Pregnancy.
9. Develops a second malignancy (except for non-melanoma skin cancer or cervical carcinoma in-situ) that requires treatment, which would interfere with this study.
10. The patient may choose to withdraw from the study at any time for any reason.
11. General or specific changes in the patient's condition that render the patient unacceptable for further treatment in the judgment of the investigator.
12. Severe non-compliance to protocol as judged by the investigator.
13. Lost to follow-up.
14. Death.
15. Closure of study by PrECOG.

Patients who discontinue study treatment early should be followed for response assessments and survival, if possible. Follow-up will continue per Section 10, as applicable.

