## 9 Measurement of Effect

Response assessments will require a bone marrow aspirate/biopsy to be performed. The 2017 European LeukemiaNet (ELN) recommendations will be used to assess response.

End of Cycle = Count Recovery

A bone marrow aspirate/biopsy is required on all patients on Day 21 (+/- 1 day window; delays due to holidays, weekends, or other unforeseen circumstances will be permitted) after initiating the first cycle of induction. Patients who have residual disease will be eligible to receive a second cycle of induction identical to the first (Section 10).

A repeat bone marrow aspirate/biopsy should be done to assess for response and MRD upon count recovery (Absolute Neutrophil Count (ANC)  $\geq$  1000/mm^3, platelets  $\geq$  100,000/mm^3) but no later than Day 60 after initiation of the cycle of induction therapy (i.e., Day 60 or patients who receive one cycle of induction and Day 84-105 for patients that receive 2 cycles of induction. (MRD sample will be obtained by Day 60 on all patients even if counts have not recovered. The only exception is a patient who has been declared a relapse based on blood counts).

Patients who do not achieve a CR or CRi by Day 60 after initiation of the last cycle of induction therapy will be removed from study.

Patients are not eligible to proceed to Consolidation unless bone marrow samples are obtained for MRD at the time of CR/CRi.

A bone marrow aspirate/biopsy is also required at the end of the first Consolidation cycle to assess disease and MRD status.

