##### **4.4.2. Discontinue Treatment**

Patients who do not achieve a CR or CR with incomplete hematologic recovery (CRi) by Day 60 if one cycle and Day 84-105 if 2 cycles of induction therapy will be removed from study.

Patients who achieve CR or CRi can proceed to post remission consolidation therapy on study or may proceed to allogeneic transplant if desired.

Patients who go to transplant or any other non-protocol leukemia directed therapy will complete an end of treatment visit and will be followed for relapse and survival only.

Reasons that a patient may discontinue treatment in a clinical study are considered to constitute one of the following:

1. Failure to achieve CR or CRi after 1- 2 cycles of induction.
2. Patient requires treatment with therapy not allowed per protocol, or patient goes on to receive HSCT.
3. Recurrence of disease or documented progression of disease.

4. Intercurrent illness that prevents further administration of treatment per investigator discretion.
5. Unacceptable adverse events.
6. Investigator and/or patient discontinue chemotherapy.
7. Pregnancy.
8. Develops a second malignancy (except for non-melanoma skin cancer or cervical carcinoma in-situ) that requires treatment, which would interfere with this study.
9. The patient may choose to withdraw from the study at any time for any reason.
10. General or specific changes in the patient's condition that render the patient unacceptable for further treatment in the judgment of the investigator.
11. Severe non-compliance to protocol as judged by the investigator.
12. Lost to follow-up.
13. Death.
14. Closure of study by PrECOG.

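### Patients without CR/CRi are described as removed from the study, which conflicts with the survival follow-up rules and leaves OS open to informative censoring

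*Protocol*

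**What the plan says.** Five places take patients without CR/CRi off the study rather than off treatment.

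- Protocol 5.2.1 does so twice. The first sentence covers patients without CR/CRi "by Day 60 if one cycle and Day 84-105 if 2 cycles of induction therapy will be removed from study". The second reads "Patients who do not achieve CR/CRi are removed from study".
- Protocol 9 says that those without CR or "CRi by Day 60 after initiation of the last cycle of induction therapy will be removed from study".
- SAP 4.4.2 repeats the 5.2.1 rule ("Day 84-105 if 2 cycles of induction therapy will be removed from study"), and SAP 5.2 repeats the Protocol 9 rule.

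Other text keeps patients in follow-up.

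- Protocol 7.2 sets a schedule from end of treatment, for progression and survival, until death or study closure. It has no exception for induction failure. Protocol 10 (footnote 25), SAP 4.4.3 and SAP Appendix I (footnote 23) repeat it.
- The same four places add a narrower sentence. In 7.2 it reads "If a patient is removed from treatment for reason(s) other than progression or full consent withdrawal, follow for survival/relapse until death or study closure".
- Protocol 7.3 lists failure to reach CR/CRi after two cycles as a reason to stop study treatment (item 2). It adds: "Patients who discontinue study treatment early should be followed for response assessments and survival, if possible".
- Protocol 5.2.1 also says that patients who go to transplant or other leukemia therapy are followed for relapse and survival.

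OS runs from randomization to death and is censored at last contact (Protocol 12.2.2, SAP 7.6.7).

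**The concern.** A site that reads 5.2.1 on its own sees one group removed and a different group, those going to transplant or other therapy, followed for relapse and survival. If contact ends because induction failed, OS is censored at about Day 60, or Day 84-105 after two cycles, and the reason for censoring is itself a strong predictor of death. Kaplan-Meier and log-rank methods assume that this is not so.

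The direction matters for this trial. A drug that raises the remission rate should improve OS partly by leaving fewer refractory patients. If those patients drop out of the risk set in both arms, that part of the benefit can no longer be seen.

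**Working it through.** **1. The plan's own figure.** The documents state no OS power and no OS event target. OS is analysed when about 110 EFS events have occurred. Schoenfeld's formula with HR 0.62, one-sided 0.05 and 80% power gives 4 × (1.645 + 0.842)² / (ln 0.62)² = 108.2, rounded up to 109, so the stated 110 is reproduced. The main EFS analysis dates induction failure to day 1, so this trigger does not depend on later follow-up of failures.

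**2. Do the follow-up rules cover the removed patients?**

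| Text | Covers a patient alive without CR/CRi? |
|---|---|
| General schedule, 7.2 | Yes, no exception, but it starts from end of treatment and does not mention removal from study |
| Narrower sentence, 7.2 | Yes if the reason is not progression, and it speaks of removal from treatment |
| 7.3 item 2; primary refractory disease in 9.6 | Only after two cycles; the removal rule in 5.2.1 also applies after one |
| SAP 4.4.2 item 1 | After one or two cycles, which differs from 7.3 item 2; the two must be reconciled |
| 7.3 closing paragraph | Yes, but only 'if possible' |
| 7.1 | Induction failure is not listed; the only disease-based reason is progression, including clinical progression |

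A failure whose blasts rise enough to meet 9.7, or whom the site records as clinical progression under 7.1, falls inside the exception in the narrower sentence. Only the general schedule and the 7.3 closing paragraph then apply.

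**3. How many patients.**

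- Phase 1 FLT3-mutated CRc at 80 mg/day or more (Protocol 1.3.4): 28/31. Failures 3/31 = 9.7%, and 170 × 3/31 = about 16.
- General CR range of 50-80% (Protocol 1.2): 170 × 0.20 = 34 and 170 × 0.50 = 85. These are upper bounds for that range, because they leave out CRi, which counts as success here, and include induction deaths, which precede any removal.

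**4. Effect on OS if these patients really were lost (illustration).** Assumptions that are not in the documents:

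- A fraction f is alive without CR/CRi at month 2.
- Their median survival from then is 7.2 months, range 4 to 10. The 7.2 is the 218-day median quoted in Protocol 1.3.4 for relapsed/refractory FLT3-mutated patients.
- Remitters have 70% 2-year OS with a constant hazard, so 97.07% are alive at month 2.

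Formulas at 24 months:

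- True OS = (1 − f) × 0.70 + f × exp(−ln 2 × 22/7.2) = (1 − f) × 0.70 + f × 0.120.
- Kaplan-Meier with failures censored at month 2 = [1 − (1 − f) × 0.0293] × (0.70/0.9707).

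| f | True OS | Estimated OS | Overstatement (points) | Range for median 10 to 4 months |
|---|---|---|---|---|
| 10% | 64.2% | 70.2% | 6 | 5 to 7 |
| 20% | 58.4% | 70.4% | 12 | 10 to 14 |
| 30% | 52.6% | 70.6% | 18 | 15 to 21 |
| 50% | 41.0% | 71.1% | 30 | 25 to 35 |

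For two arms that differ only in failures, 30% against 15%, true 2-year OS is 52.6% against 61.3%, a gap of 8.7 points. With failures censored the estimates are 70.6% and 70.3%, and the gap is gone.

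**The case against.** A reader might infer that, read literally, the protocol gives up OS in its refractory patients, because removal plus the exception for progression leaves nobody following them. The documents do not support this.

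- The general schedule in 7.2 has no such exception.
- Failure to reach CR/CRi is not progression in this protocol. Section 9.6 (treatment failure) is separate from 9.7 (progressive disease), and 7.3 item 2 is separate from item 4. The narrower sentence in 7.2 therefore normally orders follow-up of induction failures.
- The 5.2.1 sentence on transplant and other leukemia therapy covers a refractory patient who receives salvage treatment. Its word 'only' limits what is collected, not who is followed.
- The removal sentences stand in the treatment plan, in the response section and, in the SAP, under a heading about discontinuing treatment. That context suggests going off treatment.

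A reader might also say that the earliest deaths are lost. They are not: deaths during induction come before any removal and count in OS.

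All of this stands, and it makes continued follow-up the likely intention. It does not remove the conflict. The same patients are off study in five places and followed in others. One-cycle failures lack an explicit entry in 7.3, survival follow-up there is qualified, and a failure recorded as progression meets the exception.

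**Conclusion.** This is a wording conflict with a real but conditional risk to OS. No stated figure is wrong because of it, and the primary endpoint and the main EFS analysis are unaffected. OS is a secondary endpoint without stated power.

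The exposed group is the patients alive without CR/CRi at Day 60 or Day 84-105. The estimate of about 16 of 170 rests on small phase 1 data with gilteritinib only, so the midostaurin arm may differ. The 34 to 85 rests on a general CR range and overstates the count for the reasons given above.

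The overstatement of 2-year OS by about 5 to 35 points assumes that every such patient is lost at Day 60, together with the survival assumptions listed. It is what the wording would permit if all sites acted on it, not a forecast. The bias tends to reduce or hide an OS difference that arises through remission. Because the correction is nearly free, it should be made.

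**What to change.** 1. In Protocol 5.2.1 (both sentences), Protocol 9, SAP 4.4.2 and SAP 5.2, replace the removal wording with: 'removed from study treatment and followed for survival per Section 7.2'.
2. In Protocol 7.2, Protocol 10 footnote 25, SAP 4.4.3 and SAP Appendix I footnote 23, reword the narrower sentence to: 'If a patient is removed from treatment for any reason other than full consent withdrawal, follow for survival (and relapse, if applicable) until death or study closure'. Striking only the mention of progression is not enough, because what remains could be read as ordering follow-up after full consent withdrawal. All four places must match.
3. In the closing paragraph of Protocol 7.3, drop 'if possible' where it applies to survival.

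The cost is wording in the two documents and a reminder to sites. Sample size, the 110-event target, treatment and visit schedule stay as they are.

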#### 5.2.2 Consolidation

Patients deemed suitable by the treating investigator may proceed to allogeneic TRANSPLANT at any time after induction or after 0-4 cycles of chemotherapy consolidation.

Patients will continue to receive the same study drug (gilteritinib or midostaurin) assigned during induction for consolidation.

**NOTE:** Patients are not eligible to proceed to consolidation on study unless bone marrow samples are obtained for Minimal Residual Disease (MRD) at the time of CR/CRi.

#### **Consolidation Cycle 1**

Patients who achieve a CR or CRi and have no residual significant toxicities from the induction course are eligible for further protocol therapy. In general, consolidation therapy should start within 1 month of documentation of CR/CRi, after the resolution of any non-hematologic toxicity of previous chemotherapy ( $\leq$  Grade 1 or baseline). Patients must have maintained peripheral blood evidence of a remission as defined in Section 9 and must have an ANC  $\geq 1000/\text{mm}^3$ . For patients who have not recovered from the toxicities of chemotherapy within 30 days of documentation of remission, and thus require additional time, a repeat marrow should be obtained to confirm remission and PrECOG must be contacted for approval to continue on study.

**NOTE:** Patients who achieve a CRi post remission therapy are eligible to proceed to consolidation once their ANC recovers to 1000/mm^3 even if that happens more than 60 days after the initiation of their last induction cycle.

#### **ARM A**

- **Cytarabine** 3 g/m2\* over approximately 1-3 hours every 12 hours (+/- 2 hour window) on days 1,3,5 or days 1-3 for a total of 6 doses for up to 4 cycles
- **Gilteritinib** 120 mg orally QD x 14 days beginning on day 8 of each cycle (up to 4 cycles)

#### **ARM B**

- **Cytarabine** 3 g/m2\* over approximately 1-3 hours every 12 hours (+/- 2 hour window) on days 1,3,5 or days 1-3 for a total of 6 doses for up to 4 cycles
- **Midostaurin** 50 mg orally BID x 14 days beginning on day 8 of each cycle (up to 4 cycles)
- \* For patients age ≥ 55 or patients with decreased creatinine clearance recommend reducing consolidation cytarabine dose to 1.5 g/m^2.

A repeat bone marrow aspirate/biopsy is required at the end of the first consolidation cycle for repeat response assessment and MRD testing.

#### **Consolidation Cycle 2-4**

Patients must have maintained peripheral blood evidence of a remission as defined in Section 9. Consolidation Cycle 2-4 should commence within 2 weeks following recovery of peripheral blood counts after previous consolidation. Patients who do not begin consolidation Cycle 2-4 within 30 days of recovery from previous cycle are ineligible for further protocol therapy.

#### **ARM A**

- **Cytarabine** 3 g/m2\* over approximately 1-3 hours every 12 hours (+/- 2 hour window) on days 1,3,5 or days 1-3 for a total of 6 doses for up to 4 cycles
- **Gilteritinib** 120 mg orally QD x 14 days beginning on day 8 of each cycle (up to 4 cycles)

#### **ARM B**

- **Cytarabine** 3 g/m2\* over approximately 1-3 hours every 12 hours (+/- 2 hour window) on days 1,3,5 or days 1-3 for a total of 6 doses for up to 4 cycles
- **Midostaurin** 50 mg orally BID x 14 days beginning on day 8 of each cycle (up to 4 cycles)
- \* For patients age ≥ 55 or patients with decreased creatinine clearance recommend reducing consolidation cytarabine dose to 1.5 g/m^2.

If there is a delay in starting FLT3 inhibitors in Arm A or Arm B (due to obtaining drug, i.e. insurance, formulary, etc.), the FLT3 inhibitor will need to stop after Day 21 dose. No missed doses will be made up.

Patients will go off treatment at the time of transplant or any non-protocol leukemia directed therapy after completion of the end of treatment visit, and will be followed for relapse and survival only.

5.2.3 Arm A: Gilteritinib Administration

Gilteritinib 120 mg tablets (three 40 mg tablets) are taken once daily by mouth on days 8-21 (if chemotherapy were to have begun in the evening, then it is possible that the scheduled gilteritinib administration on day 8 may occur on calendar day 9). Patients will be instructed to take the daily gilteritinib with water as close to the same time each morning as possible. Tablets should not be chewed, crushed or broken.

Gilteritinib will be self-administered at home when patients are not hospitalized. If a patient forgets to take a dose in the morning and are within 6 hours of the planned dosing time, they should be instructed to take their dose. If the patient forgets to take their daily dose and are more than 6 hours has passed the planned dosing time, they should be instructed to wait for the next morning to dose. If vomiting occurs after dosing, the patient should not receive another dose, but wait until the next morning to dose.

When patients are hospitalized for treatment (i.e. induction, aplasia or events), gilteritinib will be administered per site procedures for inpatient study management. Instructions to patients and study staff regarding the above recommendations for administration should be included in orders or related patient record documentation, including drug handling and disposal.

Patient compliance for gilteritinib administration will be assessed by pill counts and IRB reviewed medication diary provided to sites. Bottles containing gilteritinib tablets will be given to patients for self-administration, when not hospitalized, and at scheduled visits. Previously distributed bottles will be returned to the study site and tablets counted by the study staff. Investigational product accountability will be maintained on the drug accountability record as per regulatory requirements.

Any discrepancy will be reviewed with the patient during the visit and documented as needed. The medication diary will be maintained in the patient records and available for review at site monitoring visits.

Dose reductions are permitted (Section 6). Missed doses are not made up. Assigned treatment should continue through induction and consolidation cycles until unacceptable toxicity occurs, or the patient meets a treatment discontinuation criterion as provided in Section 6 and/or Section 7.3.

